1.0 Background

Peripheral arterial disease (PAD) is characterized by atherosclerotic obstruction of the arteries in the lower extremities and affects approximately 10% of individuals older than 65 years. The most common clinical presentation of PAD is intermittent claudication (IC), defined as leg pain caused by insufficient blood flow during walking. Individuals with IC have severe exercise intolerance and markedly reduced levels of daily ambulatory activity. It is estimated that up to 40 million people worldwide suffer from IC. Despite the increasing prevalence of this condition, few medical therapies improve mobility and exercise tolerance in these patients. Cilostazol is the only effective medication available to treat IC. Unfortunately, this drug has multiple side effects, and the overall improvement in walking performance after long-term treatment is small. Supervised treadmill exercise is the best single treatment for IC, but the need for frequent visits to a clinical facility over an extended time period makes this option challenging for the vast majority of patients. Endovascular and surgical interventions are also effective alternatives for patients that do not respond sufficiently to medical therapy; however, these procedures are costly, only applicable to patients with certain lesion types and are associated with a high risk of restenosis. An urgent need remains for the development of novel, non-invasive strategies that are more widely accessible and eliminate the need for supervision and frequent traveling to a clinical facility.

2.0 Rationale and Specific Aims

We propose to evaluate the potential of leg thermotherapy (TT) as a non-pharmacological intervention that could improve the mobility and exercise tolerance of patients with IC. Thermotherapy (TT) is a simple, easily applicable therapy that enhances exercise tolerance in patients with chronic heart failure (CHF) by improving peripheral vascular endothelial function. Indeed, recent studies of both healthy individuals and patients with CHF have demonstrated that TT promotes a blood flow-dependent improvement in vascular endothelial function in the microcirculation and in conduit arteries. In a preclinical model of IC, TT accelerates blood flow recovery and increases vascularization in the ischemic muscles. This compelling evidence predicts that TT could have significant benefits for patients with IC. Indeed, since this intervention is non-pharmacological, there is high potential for this work to rapidly translate into clinical practice and improve patients' lives. In preliminary studies (*IRB Protocol #1409063619*), we have demonstrated application of TT for 90 min increased leg skin temperature by $\sim 7^{\circ}\text{C}$, core body temperature by $\sim 0.6^{\circ}\text{C}$ and evoked a marked reduction in systolic (~ 12 mmHg) and diastolic (~ 6 mmHg) blood pressure when compared to the control intervention (Figure 1). In addition, leg TT application induced a marked increase in leg blood flow in these patients. Based on these compelling preliminary findings, our goal is to evaluate the impact of 6 weeks (3 sessions/week) of TT treatment on vascular function and walking tolerance in patients with IC. *We hypothesize that treatment with TT will enhance walking tolerance in patients with IC by improving endothelial function and therefore increasing leg oxygenation during exercise.* Thermotherapy will be applied using water-circulating 'pants' connected to a water pump. These garments are made of a tight-fitting elastic fabric, with an extensive network of medical grade polyvinyl chloride

tubing sewn onto the fabric, and a portable pump that circulates hot water throughout the garment. This is the same system we employed in our initial study in 16 patients with IC (*IRB Protocol #1409063619*). We have shown that this system is safe and well tolerated by patients with IC. Before and after the treatment, we will examine the following outcomes: 1) cutaneous microvascular function (Laser Doppler flowmetry), 2) reactive hyperemia in the popliteal artery (phase-contrast magnetic resonance imaging of the popliteal artery), 3) calf muscle oxygenation during exercise (near-infrared spectroscopy) and 4) walking distance (6-min walking test).

[figure not shown]

Figure 1: Physiological responses to acute thermotherapy application in patients with intermittent claudication (n=16, IRB# 1409063619). Patients underwent a single 90-min session of TT or a control treatment and physiological variables were measured before, during and for 2 hours after the intervention.

3.0 Inclusion/Exclusion Criteria

Inclusion criteria

- Men and women with a stable symptomatic claudication for ≥ 6 months
- Ankle brachial index < 0.9

Exclusion criteria

- Uncontrolled Diabetes (HbA1C > 8.5 measured within 3 months prior to date of consent)
- Heart Failure
- COPD
- Critical limb ischemia (ischemic rest pain or ischemia-related non healing wounds or tissue loss)
- Prior amputation
- Exercise-limiting comorbidity (i.e., angina, chronic lung disease, or arthritis)
- Recent (<3 months) infrainguinal revascularization (surgery or endovascular revascularization) or revascularization planned during study period.
- Plans to change medical therapy during the duration of the study
- Active cancer
- Chronic kidney disease (eGFR <30 by MDRD or Mayo or Cockcroft-Gault formula).
- HIV positive, active HBV or HCV disease.
- Presence of any clinical condition that in the opinion of the principal investigator makes the patient not suitable to participate in the trial.
- Peripheral neuropathy, numbness, or paresthesia in the legs.
- Morbid obesity BMI > 36 or unable to fit into water-circulating pants.
- Open wounds or ulcers on the extremity.

As this study involves MR imaging, patients that have contraindications to MRI will be included in the study but will not be allowed to participate in the MRI procedure. Information about biomedical devices that may pose a risk to patients undergoing MRI is available on the Internet at www.MRIsafety.com. These exclusions include:

- Cardiac pacemaker
- Implanted cardiac defibrillator
- Aneurysm clips
- Carotid artery vascular clamp
- Neurostimulator
- Insulin or infusion pump
- Implanted drug infusion device
- Bone growth/fusion stimulator
- Cochlear, otologic, or ear implant
- History of claustrophobia or who are unable to lie flat or who do not fit inside the bore of the scanner

4.0 Enrollment/Randomization

Patients that fulfill the inclusion criteria and are interested in participating in the protocol will receive detailed instructions about the experimental set-up and

measurements and will be given a consent form. Once deemed eligible, patients will be asked to complete the baseline assessment. After the initial testing is complete, patients will be randomly allocated into one of two groups: low-heat therapy (control) and high-heat therapy. Medical devices and alternative therapies, such as massage and thermal-treatments have shown to be associated with high placebo responses (1). In order to control for this important psychological response, it is imperative to incorporate an appropriate placebo/sham intervention (1). In the present study, we will adopt strategies to minimize the potential confounding effect of psychological and perceptual responses to heat therapy. First, participants will be informed that the purpose of the study is to compare two ‘intensities’ of heat treatment. In the low-heat group, water at 33°C will be circulated through the garment during the treatment sessions. In our initial study (*IRB Protocol #1409063619*) we observed that this strategy evokes a small increase (~0.9°C) in leg skin temperature. In the high-heat group, hot water will be circulated through the garment during the treatment sessions with the goal of increasing skin temperature to 40°C, as observed in our initial study. A random allocation software (Research Randomizer, Social Psychology Network, <http://www.randomizer.org/>) will be used to perform the randomization.

5.0 Study Procedures

After enrollment, subjects will be asked to complete two experimental sessions for baseline testing. The procedures involved in each visit, location and estimated duration are listed on Table 1. On **visit 1**, demographic and anthropometric characteristics from participants will be initially recorded. Subjects will then be asked about comorbid conditions, claudication history, and current medications and will fill out two questionnaires to assess generic (36-item Short-Form Health Survey) and disease-specific (Walking Impairment Questionnaire) quality of life. Next, subjects will be escorted to the examination room and will be asked to rest quietly for 15 min in the supine position. During this time, four NIRS (near infrared spectroscopy) sensors (Figure 2) will be attached to subjects’ two fingertips and two toes (left and right). These sensors are the same as the pulse oximeters used regularly in the hospital. We will monitor the blood flow during these 15 minutes while subjects are resting. After this rest period, systolic blood pressure will be measured in the arms (brachial artery) and ankles (posterior tibial and dorsalis pedis arteries) for the determination of the ankle brachial index. Subjects will then be familiarized with the 6-min walking test. A near-infrared spectroscopy (NIRS) system will be placed on the calf of the most symptomatic leg for monitoring leg oxygenation during the test. This exercise test consists of walking back and forth along a 100-ft corridor for 6 min. This session will be performed at the CTSI’s Clinical Research Center on the 5th floor of Goodman Hall and is expected to last approximately 2 hours.

Figure 2: Multichannel NIRS used to monitor the blood flow at two toes and two fingertips.

Visit 2 will involve the assessment of the primary study outcomes, including vascular function and exercise tolerance. This session is expected to last approximately 4 hrs. Subjects will be asked to fast overnight prior to attending this session but will be permitted to take their usual morning medication regimen. The first exam will be the assessment of leg blood flow responses to circulatory occlusion (reactive hyperemia) using magnetic resonance imaging. This test will be performed at the Imaging Research Facilities in the basement of Goodman Hall. Next, subjects will be escorted to the CTSI's Clinical Research Center on the 5th floor. Subjects will initially be asked to lay supine and a nurse will place a catheter in one antecubital vein in the arm for venous blood sampling. After 10 min of rest, systolic blood pressures in the arms and in the ankles will be measured for the determination of the ankle-brachial index. Once the measurements are complete, a blood sample (20 ml) will be taken and the catheter will be removed. Next, subjects will be instrumented with laser Doppler probes placed inside local heaters for the assessment of cutaneous vascular reactivity. Two probes will be placed on the front portion of the most symptomatic leg and secured in place with tape. The sites where the probes are placed will be marked with a pen to allow for consistent placement in the second and third outcome measurement visits. The protocol consists of heating a site in the skin and measuring the changes in cutaneous red blood cell flux in response to the thermal challenge. Blood pressure and heart rate will be monitored during the test. This procedure will last approximately one hour. Next, the patients will perform the 6-min walking test. A near-infrared spectroscopy system, which measures skeletal muscle oxygenation, will be placed on the calf of the most symptomatic leg, secured in place with tape and covered with aluminum foil and a black Velcro strap. Similar to the laser Doppler probes, pen marks will be used identify the location of the probe. Subjects will be asked to walk back and forth along a 100-ft corridor for 6 min and report when the pain first appears. After the test is completed, subjects will be asked to grade the severity of the pain in the most symptomatic leg using the Borg-scale.

Visit #	Procedures	Location	Duration
1	
 1) Medical History and Physical Examination 2) Quality of life assessment 3) Measurement of ankle-brachial index 4) Familiarization with the 6-min walking test 	CTSI's Clinical Research Center at Goodman Hall	2 hrs
2	
 1) Leg MRI (reactive hyperemia) 2) Catheter placement and venous blood draw 3) Measurement of ankle-brachial index 4) Assessment of cutaneous vascular function 5) 6-min walking test 	Imaging Research Facilities and CTSI's Clinical Research Center at Goodman Hall	4 hrs

Table 1: Procedures involved, location and estimated duration of visits 1 and 2.

After the baseline assessment is complete, subjects will be randomly allocated to one of two groups using a random allocation software. Participants will be asked to

attend **3 treatments sessions/week for 6 consecutive weeks**. These sessions will be conducted at the CTSI’s Clinical Research Center at Goodman Hall and will last approximately 110 min. A research coordinator will supervise the patients during the sessions. On each session, subjects will initially have their body weight and blood pressure measured and recorded. Next, patients will be asked to change into the water-circulating pants (Figure 3) and lay in semi-recumbent position. The garments will be connected to the water pump and the treatment will be applied for 90 min. In the high-heat group, hot water will be circulated through the garment with the goal of increasing skin temperature to 40°C, while thermoneutral water (33°C) will be used in the low-heat group. Subjects will be allowed to drink water ad libitum during the sessions but will not be allowed to consume food. At the end of the session, body weight and blood pressure will once again be recorded. The research coordinator will measure temperature (sublingual measurements) and blood pressure every 15 minutes during the treatment and will also inspect the skin in the legs to look for potential signs of injury or adverse reactions to the treatment. The subject will be asked to complete a heat sensation scale every 15 minutes during the treatment. The research coordinator will clean the garment after each use using a hospital-grade disinfectant spray. The garment will also be washed in a washing machine every week.

Figure 3: Water-circulating garment system for thermotherapy application

Outcome measurements will be repeated after 9 sessions (3 weeks) and at the end of the treatment period (18 sessions). The protocol for these visits will be similar to visit 2, with the addition of quality of life assessment. The procedures involved are detailed on table 2. This visit is expected to last approximately 4.5 hrs. Subjects will be asked to fast overnight prior to attending this session but will be permitted to take their usual morning medication regimen.

Visit #	Procedures	Location	Duration
3 and 4	1) Leg MRI (reactive hyperemia) 2) Catheter placement and venous blood draw 3) Measurement of ankle-brachial index 4) Quality of life assessment 5) Assessment of cutaneous vascular function 6) 6-min walking test	Imaging Research Facilities and CTSI’s Clinical Research Center at Goodman Hall	4.5 hrs

Table 2: Procedures involved, location and estimated duration of visits 3 and 4.

Outcome Measures:

Reactive Hyperemia in the Popliteal Artery: Blood flow in the popliteal artery of the most symptomatic leg will be measured using MRI. We employed this technique in our initial study (IRB Protocol #1409063619). After the knee coil and the occlusion cuff are positioned on the most symptomatic leg, participants will be allowed to rest quietly for 15 min. Resting leg blood flow measurements and brachial systolic blood pressures will be completed every 5 min during this period. Next, a blood pressure cuff firmly wrapped around the lower thigh will be inflated to 75 mmHg above systolic blood pressure, or 250 mmHg, whichever is lower, for 5 min (8). Hyperemic flow will be measured for 10 min after cuff deflation. Flow reserve will be defined as the absolute difference between maximum hyperemic flow after cuff release and resting flow (9).

Cutaneous Microvascular Function: Laser-Doppler flowmetry probes, seated in the center of local skin heaters (Moor Instruments, UK), will be used to measure red blood cell flux, an index of skin blood flow (SkBF). Baseline SkBF will be recorded for 10 min after which local skin temperature will be increased to 39°C (0.1°C/s) and maintained at this level until a plateau is achieved (~40 min). Next, the local skin temperature will be elevated to 43°C, to induce maximal vasodilation. Cutaneous vascular conductance (CVC) will be calculated as laser-Doppler flux divided by mean arterial pressure (MAP), measured throughout the study via brachial artery oscillation, and normalized to maximal vasodilation (%CVC_{max}) (10, 11).

6-min Walking Test.: Participants will receive standardized instructions and will be asked to walk the greatest distance possible by walking back and forth along a 100-ft corridor for 6 min (4).

Measurement of Muscle Oxygenation: The microvascular oxygenation status of the gastrocnemius muscle of the most symptomatic leg will be monitored with near-infrared spectroscopy (NIRS), as described recently by our group (7). The optode holder of a portable NIRS system (The PortaMon Mk II, Artinis Medical Systems, Netherlands) will be placed on the medial gastrocnemius, and the concentration of deoxygenated hemoglobin + myoglobin [deoxy-Hb+Mb] will be measured continuously during the 6-min walking test (7).

Quality of life assessment: The 36-item Short-Form Health Survey domain scores for physical functioning, physical role function (i.e., limitations due to physical problems), bodily pain, and general health perceptions on a scale from 0 (severe limitation) to 100 (no limitation). In addition, self-reported ambulatory ability will be obtained with a validated questionnaire for PAD patients that assesses ability to walk at various speeds and distances and to climb stairs.

Potential risks to subjects:

6-minute walking test: Exercise-induced pain is a hallmark feature of intermittent claudication and therefore exercise tests are used as a diagnostic tool as well as well for the assessment of claudication severity and functional status of the patient (4). Typically patients experience ischemic pain in the foot, calf, thigh or buttocks during the test. The

pain is temporary and subsides within a couple of minutes after the test is terminated (4). The 6-minute walk test has been validated as an outcome measure and is increasingly recognized as a meaningful outcome measure in patients with PAD (4). The tests will be performed according to available guidelines from the American Thoracic Society (3). When performed following these guidelines, the 6-minute walking test is reported to be very safe and reflect walking in the daily life of the patients (4). However, there is a chance that patients may experience: 1) chest pain, 2) intolerable dyspnea, 3) leg cramps, 4) staggering, 5) diaphoresis, and 6) dizziness. The investigators will monitor the patients closely to test. Patients will be asked to stop walking and sit on a chair if any of these symptoms occur.

Leg heating: Hot water (47-50°C) will be perfused through the water-circulating garment with goal to increase skin temperature in the calf to 40°C. It is possible that the tubes in contact with the skin could cause discomfort due to a sensation of warmth/heat. Should the tubing that is in contact with the skin cause discomfort we will readjust the suit or turn down the temperature of the water. Ninety minutes of heating will likely lead to skin redness and flushing, which are typical responses to local heating. These effects are temporary and will fade once the heating stimulus is terminated. Once instance of skin being burned to the point of blistering has occurred. The research coordinator will examine the patient's skin during each treatment session for potential signs of injury or adverse reactions to the treatment.

A sophisticated, research-grade heated bath circulator will be used to circulate water through the garment. The actual device we use (SC100) and its technical specifications are displayed in the document entitled "SAHARA S21 Stainless-Steel Heated Bath Circulators." The temperature stability of this heated bath circulator is 0.02°C. This is a remarkably small variation, which supports the notion that there are no risks of sudden oscillations water temperature.

The actual temporal behavior of skin temperature during 90-minutes of thermotherapy application is shown on the figure on page 4 of the protocol. There are no abrupt changes in temperature. The response follows an exponential rise to a peak of around 39.5°C at 90 minutes. This temperature is safe and far below the temperature required to burn the skin, which is typically above 43°C.

Our initial study revealed that the proposed protocol leads to a progressive increase in leg skin temperature from a baseline of 33°C to ~39.5°C. A research coordinator will supervise each treatment session. If the patient experiences any discomfort or burning sensations, the coordinator will readjust the suit or turn down the temperature of the water. Subjects will be reminded to remain in a semi-recumbent position during treatment and will also be asked to rate heat sensation every 15 minutes using a thermal sensation scale to monitor for excessive heat levels on the skin. If subject reports a grade of 3 ("Hot") or above, or any discomfort, the coordinator will readjust the suit and turn down the temperature of the water. If, after reducing the temperature and readjusting the suit the patient again reports a grade of 3, we will keep repeating the aforementioned steps until the score drops down and the patient feels comfortable. Water temperature

will be assessed and recorded every 15 minutes using the temperature display on the pump.

In preliminary experiments we observed that thermotherapy application induces a minor reduction in blood pressure in some patients. The research coordinator will measure blood pressure prior to and every 15 minutes throughout the application. If the patients experience dizziness, lightheadedness or any other symptom of hypotension, the therapy will be terminated and the participant will be placed supine with the legs elevated. Blood pressure will be checked every 5 minutes until the symptoms disappear and blood pressure returns to baseline levels.

Venous blood sampling: During catheter insertion there is a risk of pain from the needle. Bleeding, local swelling, bruising and formation of a hematoma might also occur around puncture site. By using appropriate phlebotomy techniques, the risks associated with catheter placement and repeated sampling are minimized.

Blood pressure measurements: There are no risks associated with the blood pressure measurements.

Measurement of calf muscle oxygenation: There are no risks associated with blood pressure measurements.

MRI scan: Potential risks associated with MR imaging include:

- Claustrophobia: the confining conditions of the MR scanner can cause claustrophobia. If the patient experiences claustrophobia the scan will be stopped.
- Nerve stimulation: Some subjects undergoing the rapid scanning procedures which will be used in this scan have experienced minor nerve stimulation effects, such as muscle twitches and tingling sensations.
- Hearing: The MR scanner produces tapping sounds during operation, which may reach objectionable levels. To minimize any discomfort, subjects will be provided with disposable earplugs or headphones
- Collision hazard: The magnetic field near the MR Scanner is strong enough to attract objects containing iron with great force. Near the magnet this force can be strong enough to pull objects in and cause them to fly down into the magnet. Such objects can become projectiles that can cause injury or death. We have established a security zone to prevent objects containing iron from coming into proximity of the magnet.
- Radio-wave effects: If metal wires or electrodes, such as electrocardiograph (ECG) leads are attached to a person being imaged, the radio-wave energy radiated by the imaging coils of the MR scanner may induce sufficient electrical currents in the wires to cause burns where the electrodes or wires contact the skin. The scanner operator is well aware of this risk and knows the proper methods to use to avoid this problem.

Reactive hyperemia: Inflation of a cuff around the thigh to supra-systolic pressures (75 mmHg above brachial systolic blood pressure or 250 mmHg) for 5 min to provoke

ischemia might cause discomfort in some subjects, including pain, numbness and tingling in the tissue located downstream from the occlusion site. These sensations are temporary and disappear immediately after cuff deflation.

6.0 Reporting of Adverse Events or Unanticipated Problems involving Risk to Participants or Others

If the patient is injured due to participation in this study, he/she will be instructed to contact the study investigators. Patients will also be advised to contact the Human Subject Office at Indiana University if they have questions about their rights while taking part in the study.

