8.0 Statistical Considerations

Sample size was estimated based on the ability to detect a significant change in 6-min walk distance from baseline to 6 weeks in the TT-treated group as compared to the control group. The studies of McDermott and co-workers (5) and Gardner and co-workers (2), which investigated the impact of home-based exercise training on walking tolerance in patients with IC, were used as a reference for the sample size calculations. We estimated the variance of improved walk distance by the MSE of Table 3 in the study of Gardner et al (2), which is 48.69 meters. Since both studies reported a non-significant change in 6-min walk in the attention-control group (95% confidence interval for McDermott's study is (-25.4 to 3.2) and for Gardner's study is (-6.33 to 14.33)), we predict that the change in 6-min walk in the control group, in our study, will be negligible (0). As pointed out by Perera et al (6), a change of 50 meters in the 6-min walk test is considered substantial and clinically meaningful in elderly subjects. Using this effect size $(50-0)/48.69$, we determined that **16 subjects per group** are needed to detect a substantial improvement by TT therapy with a power of 0.802.

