Leg thermotherapy for intermittent claudication

NCT02770547

Document Version: 12/11/2019

Statistical Analysis Plan

Demographic and clinical characteristics were summarized overall and by group. Two-sample tests, Wilcoxon Rank Sum test, Chi-square tests, or Fisher's Exact tests were used to compare the two groups. For the analysis of MRI-derived indices, absolute values were used for peak flow and flow per minute as sometimes the values reported from the machine were negative. Percentage change in peak flow is defined as $(\text{max absolute value} - \text{mean baseline absolute value}) / \text{mean baseline absolute value}$. For the outcome of 6-min walk test, the best of V1 and V2 was used as baseline. For the MRI-derived indices, the blood parameters, cutaneous microvascular function, and the experimental blood pressure, V2 was used as the baseline; while for the quality of life, V1 was used as the baseline. For physiological variables of systolic blood pressure, diastolic blood pressure, mean arterial pressure, heart rate, and temperature in the ear, change from baseline at each time point using the mean of total 18 sessions in two groups was plotted. Area under the curve (AUC), expressed as arbitrary units, for the total 90 minutes was plotted. The AUC for the change from baseline was also plotted in each session in each group. For the cutaneous microvascular function, mean arterial pressure, cutaneous vascular conductance (CVC) and MaxCVC were plotted by mean with standard error at each time point in each experimental visit; AUC for the total 14 time points were also plotted. In the experimental blood pressure, means with standard error were plotted for the change of systolic blood pressure, diastolic blood pressure and mean arterial pressure from baseline timepoint in high-heat therapy group or low-heat therapy group separately; change of AUC in systolic blood pressure, diastolic blood pressure and mean arterial pressure from baseline visit V2 were also plotted. For 6-min walk test, MRI-derived indices, blood parameters, quality of life, the AUC of cutaneous microvascular function indices, and AUC of experimental blood pressure, analyses were done with two different model types. First, linear mixed models with fixed effects for visiting time (V1 or V2, V3, V4) and intervention (high heat, low heat) were fit using the raw data. A significant interaction of time and intervention would indicate that there were differential effects of high and low heat over time. If the interaction was not significant, it was removed. In the main effects only model, a significant main effect for intervention would indicate that the two intervention groups are different (with the same magnitude of difference) across all time points (including baseline). Second, the changes from baseline to V3 and baseline to V4 were modeled with a linear mixed model. Here a significant interaction of time and intervention would mean the intervention effect was different at V3 vs V4. If the interaction was not significant, it was removed. In the main effects only model for change, a significant main effect for intervention would mean that there was an intervention effect, and it was of the same magnitude at V3 and V4. As the results were largely consistent, the results section focuses on the change score model results. Two sample t-tests were used to check whether the AUC for the change of physiological variables were different between two treatment groups. For the cutaneous microvascular function, the MaxCVC from two laser Doppler probes were compared at each timepoint using the linear mixed model with fixed effects for time point and probe, a significant interaction of timepoint and probe would indicate that the MaxCVC from two probes are different over time. The probe effects at each time point were also tested when the probe by time interaction was statistically significant at the significance level 0.05, or the main effects of probe were checked if the probe by time interaction was not statistically significant at the significance level 0.05. All analyses were performed using SAS v9.4.

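### The protocol and SAP do not agree on one primary comparison, the SAP's default test is not the comparison that was powered, and the SAP justifies the reported model by its results

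*Protocol*

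**What the plan says.** Three places bear on which comparison is primary.

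- **Protocol 5.0 (Visit 2)** uses an open-ended plural: "Visit 2 will involve the assessment of the primary study outcomes, including vascular function and exercise tolerance". Section 2.0 introduces four outcomes with "Before and after the treatment, we will examine the following outcomes" and does not rank them: cutaneous microvascular function, popliteal reactive hyperemia, calf oxygenation and walking distance.
- **Protocol 8.0** sizes the trial on one comparison: "Sample size was estimated based on the ability to detect a significant change in 6-min walk distance from baseline to 6 weeks", treated versus control. The target is 50 m, the control change is taken as zero, and 16 per group gives power 0.802. The section does not call this comparison primary.
- **The SAP** names no primary outcome. It models six families alike: 6-min walk, MRI indices, blood parameters, quality of life, cutaneous AUC and blood pressure AUC. Each gets two linear mixed models, one on raw values and one on change from baseline. In both, a non-significant time-by-group interaction is removed, and in the change model this leaves one effect common to V3 and V4. A 0.05 level appears only for the laser Doppler probe comparison. On which model to present, it says: "As the results were largely consistent, the results section focuses on the change score model results".

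**The concern.** A reader of the results needs to know which test the trial was designed around, at which visit and from which model. Section 5.0 would admit a vascular result as primary, section 8.0 points to walking at 6 weeks, and the SAP points nowhere. Two things are at stake.

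1. **The powered test may not be the one delivered.** An effect averaged over 3 and 6 weeks is a different quantity from the 6-week effect. Its power depends on how quickly benefit appears.
2. **Nothing in the documents limits what may be presented as the main finding.** With several outcomes on an equal footing, no alpha rule, and a choice of model explained by the results, a reader cannot tell how much selection lies behind a p-value. The SAP says the two models largely agreed. It does not say whether they agreed on the walk test.

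**Working it through.** **Inputs.** From protocol 8.0: difference 50 m, SD 48.69 m (the protocol calls it a variance estimated by an MSE but uses it as an SD), 16 per group. Visits: V3 after 3 weeks, V4 at end of treatment. Assumed, because the documents do not give them: two-sided alpha 0.05, and all correlations.

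**1. The plan's own figure.** Two-sample t-test, noncentral t:
- d = 50/48.69 = 1.027; df = 30; noncentrality = 1.027 × √(16/2) = 2.905.
- Power = 0.8025, against the stated 0.802. It reproduces. One-sided, it would be 0.884, so the stated figure implies one two-sided 0.05 test of the 6-week change.

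**2. The SAP's pooled effect if benefit builds up.** Assume 25 m at V3 and 50 m at V4, the same SD for both changes, and correlation r between them.
- Mean effect = (25 + 50)/2 = 37.5 m. SD of the patient average = 48.69 × √((1 + r)/2).
- r = 0.3: SD 39.26, d = 0.955, power 74%.
- r = 0.9: SD 47.46, d = 0.790, power 58%.

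These are powers of the pooled test itself. Whether the SAP reaches that test depends on the interaction: its difference is 25 m with SD 48.69 × √(2(1 − r)). That gives d = 0.434 and 22% power at r = 0.3, and d = 1.148 and 88% at r = 0.9. When the interaction is significant, the SAP does not say which visit's effect is then the result.

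The loss depends on the time course. If the full 50 m were already present at V3, the same formula with 50 m in place of 37.5 m gives 94% at r = 0.3 and 82% at r = 0.9.

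**3. Several outcomes, one 0.05 test each, any success counting.** Chance of at least one false positive = 1 − 0.95^k if independent:

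| Outcomes | Independent | Correlation 0.5 |
|---|---|---|
| 2 (the two domains in 5.0) | 9.75% | 9.0% |
| 4 (protocol 2.0) | 18.5% | 15.5% |
| 6 (SAP families) | 26.5% | not computed |

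The four and the six are different lists: the SAP does not model calf oxygenation.

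**4. Several tests within one outcome.** Null simulation, 20,000 trials, 16 per arm, baseline/V3/V4, within-patient correlation 0.5 to 0.9:
- V4 change alone: 4.9–5.4%.
- Change-model main effect alone: 4.7–5.2%.
- Raw-model interaction or change-model main effect: 7.3–8.0%. These are the two tests of differential change over time.
- Any of the four tests (interaction or main effect, either model): 14.3–15.0%.

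**5. Price of keeping more than one primary.** With Bonferroni and the walk-test effect size, 16 per group gives 70.6% power per test for two primaries (20 per group for at least 80%). For four it gives 60.1% (23 per group).

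**The case against.** The strongest reply is that section 8.0 already singles out one outcome and visit, and nothing else is powered. The Visit 2 sentence is visit logistics and may mean only the main measurements. This largely stands: the trial does have an identifiable design comparison. What remains is that neither document labels it primary, section 5.0 says otherwise, and the SAP does not carry it forward.

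Second, the reported change-score model matches the change-from-baseline endpoint in section 8.0, and two models that largely agree leave little room for selection. That also stands as far as it goes. A reader might infer that some results conflicted and that the reported p-values are biased. The documents show no differing result and no size of bias. They show only that the stated reason for the choice is the results themselves.

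Third, a reader might infer that the 5% error rate is breached, by 14% for a single outcome or far more once compounded across outcomes. The documents do not support that:

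- No efficacy alpha is stated, and no rule says that any success counts.
- The 14–15% includes a raw-model main effect that the SAP reads as a group difference present at baseline too, and a change-model interaction that it reads as V3 differing from V4. Neither is a plain efficacy test.
- Compounding over the protocol's four outcomes assumes independence, although section 2.0 hypothesises a causal chain from endothelial function through oxygenation to walking. It also counts calf oxygenation, which the SAP does not model.

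**Conclusion.** The concern holds in a limited form. Protocol 5.0, protocol 8.0 and the SAP do not agree on a primary comparison, and following the SAP as written does not necessarily deliver the V4 comparison that was powered. Under the assumed gradual benefit, the pooled effect has about 74% to 58% power against the stated 80.2%. With a full early benefit there would be no loss.

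The error-rate consequence is conditional. If any outcome may count at two-sided 0.05, it is 18.5% for four and 26.5% for six independent outcomes, and less with correlation. Within one outcome it is about 7–8% across the two tests of differential change, and about 5% for one test fixed in advance. The two-sided 0.05, the correlations and the time course are assumptions. The disagreement between documents and the results-based reason for the reported model are on the page.

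**What to change.** - State that the primary comparison is the one section 8.0 powers: change in 6-min walk distance from baseline to V4, high versus low heat, two-sided 0.05. Take it as the V4 contrast from the change-score model, with the time-by-group term kept whether or not it is significant.
- In protocol 5.0, replace the reference to primary outcomes with a neutral reference to study outcomes.
- Label V3 and all other outcomes secondary, reported as estimates with 95% confidence intervals.
- Report both models for every outcome in place of the sentence that they were largely consistent.
- Because the SAP already describes results, state plainly that the model choice and this primary label were set after the results were known. Section 8.0 is the anchor for the label. Any baseline-adjusted model would be a further choice after the data and should appear only as a labelled sensitivity analysis.

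Cost: revised wording, the V4 contrast and one extra table. No patients are added, and power for the primary test stays at 80.2% under the protocol's own assumptions. The downside is that a vascular result with p<0.05 can no longer be presented as a primary success.
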